#### **8.1.9 Accountability**

The investigator, or a responsible party designated by the investigator, should maintain a careful record of the inventory and disposition of the agent using the NCI Drug Accountability Record Form (DARF) or another comparable drug accountability form. (See the NCI Investigator's Handbook for Procedures for Drug Accountability and Storage.)

#### **8.1.10 Destruction and Return**

At the end of the study, unused supplies of ramucirumab will be either destroyed per institutional policy or returned to Eli Lilly as directed.

## 9. STUDY CALENDAR

Baseline evaluations are to be conducted within 2 weeks prior to start of protocol therapy. Scans and x-rays must be done  $\leq$ 4 weeks prior to the start of therapy. In the event that the participant's condition is deteriorating, laboratory evaluations should be repeated within 48 hours prior to initiation of the next cycle of therapy.

Assessments must be performed prior to administration of any study agent. Study assessments and agents should be administered within  $\pm$  2 days of the protocol-specified date, unless otherwise noted.

REQUIRED INFORMATION/EXAMS	Pre-Study a	Day 1 of each cycle a	Day 15 of each cycle	Restaging b	Off-Treatment c	Follow-Up (Overall Survival)
Informed consent	X					
Medical and Oncologic History	X	X	X		X	
Concurrent meds	X	X	X		X	
Physical exam (including height, weight, blood pressure, pulse)	X	X	X		X	X c
ECOG Performance Status	X	X	X		X	X c
Adverse event evaluation	X	X	X			
CBC with differential	X	X	X		X	
PT/PTT	X					
Bilirubin, ALT, AST, Albumin, Alkaline Phosphatase	X	X	X		X	
BUN, Cr, electrolytes, including Na, K, Cl, HCO 3 , Ca, Phosphate, Mg	X	X	X		X	
Urinalysis with assessment of urine protein	X	X			X	
$\beta$ -HCG d	X					
EKG f	X				X	
Radiographic evaluation b	X			X	X	X c
Chromogranin A, 24-hr urine 5-HIAA e	X			X	X	X c

a. Screening assessments must occur within 14 days of start of ramucirumab administration. Pre-registration labs may be used for Day#1 of Cycle#1 if obtained within 7 days of starting treatment. For subsequent cycles, labs must be obtained within 48 hours of start of treatment

b. Baseline scans must be performed within 28 days of start of study therapy. Restaging scans will be performed every 12 weeks until disease progression, or end of study treatment. All patients will receive an arterial and venous phase Chest/Abdomen/Pelvic CT. A liver MRI with gadolinium may be included at the discretion of the treating physician. Please note, Multiphase CT scan (chest/abdomen/pelvis) is the preferred modality for imaging.

Equivalent modalities (e.g., CXR and MRI scan of abdomen and chest) may be used at the discretion of the investigator.

- c. For patients who discontinue study treatment prior to tumor progression, physical examination, performance status, chromogranin A, and radiologic imaging studies should be performed every 12 +/- 1 weeks until tumor progression or the start of a new anticancer therapy. Patients who discontinue treatment at the time of tumor progression should be followed every 6 months +/- 1 week for survival, with chromogranin A and imaging studies at the discretion of the investigator.
- d. Serum pregnancy test (women of childbearing potential)
- e. Chromogranin A will be assessed every 12 weeks. 24-hour urine 5-HIAA will be assessed and followed as clinically indicated every 12 weeks.
- f. EKG assessments will be performed with standard 12-lead EKG equipment according to standard procedures. Abnormalities in the EKG that lead to a change in subject management (eg, dose reduced or withheld, requirement for additional medication or monitoring) or result in clinical signs and symptoms are considered clinically significant for the purposes of this study and will be recorded on the AE CRF. If values meet criteria defining them as serious, they must be reported as SAEs.

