### 1.3 Secondary Objectives

- To determine the safety and tolerability of ramucirumab in combination with somatostatin analog therapy in patients with advanced carcinoid tumors.
- To assess the overall radiographic and biochemical response rate associated with ramucirumab in combination with somatostatin analog therapy in patients with advanced carcinoid tumors
- To assess the overall survival duration of patients with advanced, progressive carcinoid tumors treated with ramucirumab in combination with somatostatin analog therapy.

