#### *Pharmacokinetics:*

Trough concentrations (or minimum concentrations [Cmin]) were collected in two Phase 3 studies (REGARD and RAINBOW) in patients with gastric cancer. Following the recommended clinical dose regimen, 8 mg/kg every 2 weeks, observed Cmin values were similar between

REGARD and RAINBOW, as noted in the table below (Investigator's Brochure, [Table 6.1](#)). The geometric mean observed trough values were approximately 50 ug/mL and approximately 60 to 70 ug/mL before the fourth and seventh doses, respectively.

**Table 6.1. Summary of Observed Ramucirumab Trough Concentrations for Patients with Advanced Gastric Cancer Following Administration of 8 mg/kg of Ramucirumab Every 2 Weeks as an IV Infusion over Approximately 1 Hour Alone (REGARD) or in Combination with Paclitaxel (RAINBOW)**

Dose Number	Trough a Serum Concentrations (ug/mL)			
	4		7	
	REGARD	RAINBOW	REGARD	RAINBOW
n PK	53	203	34	142
Geo Mean	49.5	45.0	74.4	62.8
Geo CV%	81	50	58	47

Abbreviations: CV% = percentage coefficient of variation; Geo = geometric; IV = intravenous; nPK = number of pharmacokinetic observations included in calculation.

a Trough concentrations were obtained prior to Doses 4 and 7. They also represent Cmin following Doses 3 and 6.

Pharmacokinetic data were from pooled from 8 studies including 497 patients with various malignancies for a population pharmacokinetic (PopPK) analysis. In these studies, ramucirumab was administered as a 1-hour I.V. infusion, at either 8 mg/kg once every 2 weeks on a 14- or 28-day cycle, or 10 mg/kg every 3 weeks on a 21-day cycle. The geometric mean (percentage coefficient of variation [CV%]) of PopPK model-derived estimates of ramucirumab clearance (CL), volume of distribution at steady state (Vss) and terminal half-life (t1/2) were 0.0140 L/h (29.8%), 5.5 L (14.4%), and 15 days (24.1%), respectively. These parameter estimates were consistent with those observed with other human monoclonal IgG1 (Keizer et al. 2010) antibodies. Results from the PopPK analyses indicate that the PK of ramucirumab following 8- and 10-mg/kg dose administrations were dose linear (absolute dose range: 169 to 1234 mg) and time independent.

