### 5.6 **Duration of Follow Up**

Subject survival and subsequent therapy information will be collected, preferably via office visit or telephone contact, every 6 months +/- 1 week from the date of last dose of study drug until the subject's death or until the subject is lost to follow-up, or until study closure. For patients who discontinue therapy prior to disease progression, a physical exam, performance status, Chromogranin A, and radiographic imaging will be assessed every 12 weeks +/- 1 week until tumor progression or start of new anticancer therapy.

Participants removed from protocol therapy for unacceptable adverse event(s) will be followed until resolution or stabilization of the adverse event.

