## 7.4 Expedited Adverse Event Reporting

7.4.1 Investigators **must** report to the Overall PI any serious adverse event (SAE) that occurs after the initial dose of study treatment, during treatment, or within 30 days of the last dose of treatment on the local institutional SAE form.

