### **12.4 Analysis of Secondary Endpoints**

Secondary objectives of this study are to:

- To determine the safety and tolerability of ramucirumab in combination with somatostatin analog therapy in patients with advanced carcinoid tumors. We will assess the rate of adverse events (as defined by Common Terminology Criteria for Adverse Events (CTCAE), version 4.0), associated with treatment.

Because adverse events associated with the combination of ramucirumab and a somatostatin analog have not examined previously, toxicity and adverse events will be examined in the first 10 patients who complete one cycle of therapy before expanding enrollment.

- To assess the overall radiographic and biochemical response rate associated with ramucirumab in patients with advanced carcinoid tumors. We will estimate the response rate and provide the associated 95% confidence interval.

- To assess the overall survival duration of patients with advanced carcinoid tumors treated with ramucirumab. We will use the Kaplan-Meier method to estimate the distribution of overall survival.

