## 12.5 Reporting and Exclusions

### 12.5.1 Evaluation of Toxicity

All participants will be evaluable for toxicity from the time of their first treatment.

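### No visit in the calendar looks for new adverse events after the last infusion, and the plan sets no end to adverse-event counting, so late, mainly non-serious events may be under-counted

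*Combined protocol and SAP*

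**What the plan says.** Safety is a secondary objective. Section 1.3 sets out "To determine the safety and tolerability of ramucirumab in combination with somatostatin analog therapy", and Section 12.4 gives the analysis: "We will assess the rate of adverse events", graded by CTCAE version 4.0. Section 12.5.1 fixes when counting starts but not when it stops: "All participants will be evaluable for toxicity from the time of their first treatment".

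In the Section 9 calendar, the row "Adverse event evaluation" is marked at Pre-Study, Day 1 and Day 15. It is blank at Restaging, Off-Treatment and Follow-Up. History, concurrent medication, physical examination, CBC, liver tests, chemistry, urinalysis and EKG all carry an Off-Treatment mark. On timing, the same section says: "Assessments must be performed prior to administration of any study agent".

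Other sections deal with the period after treatment:
- Section 7.4.1 requires SAEs to be reported up to and "within 30 days of the last dose of treatment on the local institutional SAE form".
- Section 7.4.2 applies a 30-day period to unexpected related Grade 2-3 events, Grade 4 events (with one exception) and all Grade 5 events.
- Section 7.4.6 requires all adverse events on the toxicity case report forms and names no cut-off.
- Section 5.6 states: "Participants removed from protocol therapy for unacceptable adverse event(s) will be followed until resolution or stabilization of the adverse event".

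**The concern.** A rate of adverse events depends on how long, and how actively, each patient is observed. Here active enquiry ends before the last infusion, while the reporting rules run on for 30 days. A new event in that interval enters the data only if someone volunteers it, if another procedure happens to reveal it, or if it is serious or graded highly enough to trigger expedited reporting.

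The loss would fall mainly on new, non-serious events, and it would push the rate downward. Because no end of counting is stated, sites could also apply different windows. Sections 5.1 and 12.4 both say that adverse events of this combination have not been examined before, so the safety description is one of the trial's main products.

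**Working it through.** The plan states no figure on this point to reproduce. The sample size of 43 and its power do not depend on it. The check is a reading of the sections against each other, followed by arithmetic for scale only.

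**Step 1. Is an evaluation scheduled after the last infusion?** The only on-treatment marks are Day 1 and Day 15, and assessments come before dosing. The evaluation on the day of the last infusion therefore precedes it. Off-Treatment and Follow-Up are blank. A patient who attends the next Day 1 or Day 15 visit and is not dosed may be evaluated about 14 days after the last infusion. That leaves 30 − 14 = 16 days of the 30-day period. A patient who does not attend such a visit has all 30 days without a scheduled evaluation.

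**Step 2. Does other follow-up fill the gap?**

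| Provision | What it covers | Seeks new adverse events? |
|---|---|---|
| 5.6, 6-monthly contact | Survival and later therapy | No |
| 5.6 and calendar footnote c, 12-weekly visits if stopped before progression | Examination, performance status, chromogranin A, imaging | Not listed |
| 5.6, removal for toxicity | The event that led to removal, followed to its outcome | Not for other patients |
| 7.4.1, 7.4.2 | Serious and certain graded events, 30 days | Duty to report once known |
| 7.4.6 | All adverse events | Duty to report once known, no end date |
| Off-Treatment visit | History, examination, laboratory tests, EKG | Indirectly |

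The last row helps in part. Under Section 7.2.1 an abnormal result is an adverse event only if it is judged clinically significant or needs treatment or further tests. At Off-Treatment the calendar does not call for that judgement. Only EKG findings are expressly sent to the adverse-event form (footnote f). No section dates the Off-Treatment visit.

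**Step 3. How long is the interval relative to observation?** The share is 30 / (30.4375 × m + 30), where m is months from first to last dose. The documents do not give time on treatment, so m is an assumption shown as a range.

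| m (months) | Calculation | Share |
|---|---|---|
| 2 | 30 / 90.9 | 33% |
| 4 | 30 / 151.8 | 20% |
| 8 | 30 / 273.5 | 11% |
| 12 | 30 / 395.3 | 8% |
| 24 | 30 / 760.5 | 4% |

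**Step 4. Is there still drug exposure?** Section 2.2.1 gives a terminal half-life of 15 days. With simple exponential decay, the fraction remaining is 2^(−14/15) = 0.52 at day 14 and 2^(−30/15) = 0.25 at day 30.

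Steps 3 and 4 show that the interval is not negligible. Neither gives a number of missed events.

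**The case against.** The strongest reply is that the reporting duty exists and only a calendar mark is missing. SAEs must be reported for 30 days and notified to the drug's manufacturer within 24 hours (7.4.1, 7.4.5). The graded events in 7.4.2 are covered for the same period, and 7.4.6 has no cut-off. The Off-Treatment visit includes history, blood pressure, blood counts, liver tests, urine protein and EKG, so hypertension, proteinuria and cytopenias would be measured there.

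Much of this stands, and it rules out three stronger readings:
- A reader might infer that nothing covers the 30 days after the last dose. Sections 7.4.1, 7.4.2 and 7.4.6 contradict that.
- A reader might infer that serious antiangiogenic events are the main loss. Perforation, major bleeding and major thromboembolic events would commonly meet the serious definition in 7.2.2 and so fall under 7.4.1. Section 6.3.10 sends every case of RPLS to SAE reporting.
- A reader might treat the half-life figures as the size of the bias. They describe residual drug, not events.

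What does not stand is the step from a duty to report to systematic detection. None of these provisions schedules a contact at which new events are sought after the last infusion, and none says when counting ends.

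**Conclusion.** The point holds in limited form. As written, the calendar leaves new-onset, mainly non-serious events after the last infusion without a scheduled evaluation, and Sections 12.4 and 12.5.1 leave the end of counting open. The adverse-event rate may be too low, and the window may differ between patients. It would go too far to say that late toxicity is under-counted: the documents give no post-treatment event rate, so the number missed cannot be computed and could be small.

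The gap can affect any patient who stops treatment. It is 30 days, or about 16 for a patient evaluated at a visit where the dose was not given. The primary endpoint, sample size and power are unaffected.

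The conclusion assumes that the blank cells are blank in the source table, which should be checked. Neighbouring rows kept their Off-Treatment marks, so a lost mark is unlikely.

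**What to change.** 1. In the Section 9 calendar, mark "Adverse event evaluation" at the Off-Treatment visit for all patients, whatever the reason for stopping.
2. State in Sections 9, 12.4 and 12.5.1 that adverse events are counted from first treatment through 30 days after the last dose, matching 7.4.1.
3. Optional: where the Off-Treatment visit falls before day 30, add a brief telephone check at day 30. The first two changes do not depend on it.

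The cost is one calendar mark, a sentence in each of the three sections, and slightly more data entry at a visit that already takes place. Reported rates may rise slightly because more events are found. The change concerns data collection only and touches no dose or treatment rule.

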## **3. PARTICIPANT SELECTION**

### **3.1 Eligibility Criteria**

3.1.1 Participants must have histologically or cytologically confirmed low- to intermediate-grade neuroendocrine tumor (carcinoid tumor).

- 3.1.2 Carcinoid tumors of any site are eligible. Patients with pancreatic neuroendocrine tumors are excluded.
- 3.1.3 Participants must have measurable disease, defined as at least one lesion that can be accurately measured in at least one dimension (longest diameter to be recorded for non-nodal lesions and short axis for nodal lesions) as  $\geq 20$  mm with conventional techniques or as  $\geq 10$  mm with spiral CT scan, MRI, or calipers by clinical exam. See Section 10 for the evaluation of measurable disease.
- 3.1.4 Locally advanced, unresectable or metastatic disease.
- 3.1.5 Patients must have evidence of radiographic disease progression within the past 12 months. Progressive disease by RECIST criteria is not required.
- 3.1.6 Age  $\geq 18$  years.
- 3.1.7 ECOG performance status 0-1 (see Appendix A).
- 3.1.8 Participants must have normal organ and marrow function as defined below:
- |                             |  |
|-----------------------------|--|
| - absolute neutrophil count | $\geq 1,000/\text{mm}^3$   |
| - platelets                 | $\geq 100,000/\text{mm}^3$   |
| - hemoglobin                | $\geq 9\text{ g/dL}$   |
| - total bilirubin           | $\leq 1.5 \times$ institutional upper limit of normal  |
| - AST(SGOT)/ALT(SGPT)       | $\leq 3 \times$ institutional upper limit of normal, or $\leq 5 \times$ institutional upper limit of normal in the setting of liver metastases   |
| - creatinine                | $\leq 1.5 \times$ upper limit of normal  |
| - urinary protein           | $\leq 1+$ on dipstick or routine urinalysis (if urine dipstick or routine urinalysis is 2+, a 24-hour urine collection for protein must demonstrate $<1000$ mg of protein in 24 hours)   |
| - coagulation function      | Adequate coagulation function as defined by International Normalized Ratio (INR) $\leq 1.5$ and a partial thromboplastin time (PTT) $< 1.5 \times$ institutional upper limit of normal. Patients on full-dose anticoagulation must be on a stable dose (minimum duration 14 days) of oral anticoagulant or low molecular weight heparin. |

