### **10.1.3 Methods for Evaluation of Disease**

All measurements should be taken and recorded in metric notation using a ruler, calipers, or a digital measurement tool. All baseline evaluations should be performed as closely as possible to the beginning of treatment and never more than 4 weeks before the beginning of the treatment.

The same method of assessment and the same technique should be used to characterize each identified and reported lesion at baseline and during follow-up. Imaging-based evaluation is preferred to evaluation by clinical examination unless the lesion(s) being followed cannot be imaged but are assessable by clinical exam.

**Clinical lesions.** Clinical lesions will only be considered measurable when they are superficial (e.g., skin nodules and palpable lymph nodes) and  $\geq 10$  mm in diameter as assessed using calipers (e.g., skin nodules). In the case of skin lesions, documentation by color photography, including a ruler to estimate the size of the lesion, is recommended.

**Conventional CT and MRI.** This guideline has defined measurability of lesions on CT scan based on the assumption that CT thickness is 5mm or less. If CT scans have slice thickness greater than 5 mm, the minimum size of a measurable lesion should be twice the slice thickness. MRI is also acceptable in certain situations (e.g. for body scans).

Use of MRI remains a complex issue. MRI has excellent contrast, spatial, and temporal resolution; however, there are many image acquisition variables involved in MRI, which greatly impact image quality, lesion conspicuity, and measurement. Furthermore, the availability of MRI is variable globally. As with CT, if an MRI is performed, the technical specifications of the scanning sequences used should be optimized for the evaluation of the type and site of disease. Furthermore, as with CT, the modality used at follow-up should be the same as was used at baseline and the lesions should be measured/assessed on the same pulse sequence. It is beyond the scope of the RECIST guidelines to prescribe specific MRI pulse sequence parameters for all scanners, body parts, and diseases. Ideally, the same type of scanner should be used and the image acquisition protocol should be followed as closely as possible to prior scans. Body scans should be performed with breath-hold scanning techniques, if possible.

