#### 10.1.4.3 Evaluation of New Lesions

The finding of a new lesion should be unequivocal (i.e. not due to difference in scanning technique, imaging modality, or findings thought to represent something other than tumor (for example, some ‘new’ bone lesions may be simply healing or flare of pre-existing lesions). However, a lesion identified on a follow-up scan in an anatomical location that was not scanned at baseline is considered new and will indicate PD. If a new lesion is equivocal (because of small size etc.), follow-up evaluation will clarify if it truly represents new disease and if PD is confirmed, progression should be declared using the date of the initial scan on which the lesion was discovered.

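### Study Calendar footnote b allows an imaging substitute that does not cover the same regions as the required CT, and no rule fixes coverage across scans, so PFS events can be missed or falsely created

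*Combined protocol and SAP*

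**What the plan says.** Footnote b of the Study Calendar (Section 9) makes three statements of different strength. The first is a requirement: "All patients will receive an arterial and venous phase Chest/Abdomen/Pelvic CT". The second softens it: "Multiphase CT scan (chest/abdomen/pelvis) is the preferred modality for imaging". The third leaves the choice open: "Equivalent modalities (e.g., CXR and MRI scan of abdomen and chest) may be used at the discretion of the investigator". The last sentence names no visits and does not name the pelvis.

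Other sections bear on what happens next:

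- Section 3.1.2 on the population: "Carcinoid tumors of any site are eligible" (pancreatic tumours are excluded).
- Section 10.1.2 asks for target lesions that represent every involved organ, and for all other disease sites to be recorded at baseline and their status noted through follow-up.
- Section 10.1.3 on consistency: "The same method of assessment and the same technique should be used to characterize each identified and reported lesion at baseline and during follow-up". For CT and MRI it adds that "the modality used at follow-up should be the same as was used at baseline".
- Section 10.1.4.3 guards against artefacts of technique or modality, but also states that "a lesion identified on a follow-up scan in an anatomical location that was not scanned at baseline is considered new and will indicate PD".
- Sections 12.1 and 12.2 make RECIST-based PFS the primary endpoint, read by the investigator, with scans every 12 weeks (Sections 9 and 10.1).

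**The concern.** Required, preferred and discretionary cannot all describe the same scan. The larger difficulty is that the listed substitute is called equivalent although it covers less anatomy, or covers part of it less well, than the CT it replaces.

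Two errors can follow, in opposite directions. If a region is left out at follow-up, progression there goes unrecorded until it is imaged or shows elsewhere, and PFS is lengthened. If a region is left out at baseline and imaged later, disease that was already present counts as progression under Section 10.1.4.3, and PFS is shortened. In both cases the recorded time depends on an imaging choice and not on the tumour.

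The trial is open-label and single-arm, and its result is set against the placebo arm of RADIANT-2 (Section 2.3). There is no concurrent arm in which the same imaging choices could balance out.

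**Working it through.** **Step 1: coverage, region by region**

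| Region | Required CT | Substitute, read literally | Substitute, if chest is a slip for pelvis |
|---|---|---|---|
| Chest | CT | x-ray and MRI | x-ray only |
| Abdomen | CT | MRI | MRI |
| Pelvis | CT | none | MRI |

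Each reading leaves one deficiency. They are alternatives; no single reading produces both.

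**Step 2: do the other rules close the gap?** Sections 10.1.2 and 10.1.3 act on lesions already identified and on modality. Neither fixes which regions are scanned. Two sequences comply with both (literal reading):

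- Baseline and all restaging by MRI of abdomen and chest with chest x-ray. The method never changes, and a new pelvic lesion is never looked for.
- Baseline as above, with MRI of the pelvis added later. The modality is unchanged, and a pelvic lesion that was present from the start is PD under Section 10.1.4.3.

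**Step 3: reproduce the planned size.** Inputs from Section 12.2: medians 8 and 12 months, one-sided alpha 0.05, power 80%, N = 43, accrual A = 24 months, follow-up F = 24 months (taken as after accrual ends). The test is not named there. I assume exponential PFS and a one-sample test on the log median.

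- Events: (1.645 + 0.842)² / (ln 1.5)² = 37.6
- Hazard under the alternative: λ = ln 2 / 12 = 0.0578
- P(event) = 1 − (e^(−24λ) − e^(−48λ)) / (24λ) = 1 − (0.2500 − 0.0625) / 1.386 = 0.865
- N = 37.6 / 0.865 = 43.5
- Power at 43: Φ(√(43 × 0.865) × 0.405 − 1.645) = 0.796

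This agrees with the stated 43 and 80%.

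**Step 4: effect of misdated events.** One scan interval is 84 / 30.44 = 2.76 months. I used simulation with 40,000 trials per setting and the Step 3 design. Affected patients either have 2.76 months added to their event time or are called PD at 2.76 months at the latest. The frequencies are assumptions; 5% and 10% of 43 are about 2 and 4 patients.

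| Setting | Log-median test | One-sample log-rank | Apparent median (months) |
|---|---|---|---|
| Null, no error: alpha | 4.0% | 4.1% | 8.0 |
| 5% one scan late: alpha | 4.7% | 4.6% | 8.2 |
| 10% one scan late: alpha | 5.3% | 5.4% | 8.3 |
| 20% one scan late: alpha | 7.1% | 7.1% | 8.6 |
| Alternative, no error: power | 79.3% | 79.6% | 12.0 |
| 2% false PD at week 12: power | 75.8% | 75.8% | 11.6 |
| 5% false PD at week 12: power | 69.5% | 69.2% | 11.1 |
| 10% false PD at week 12: power | 57.0% | 57.6% | 10.2 |

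The Monte Carlo standard error is about √(0.04 × 0.96 / 40,000) = 0.1 percentage point for alpha.

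**The case against.** The strongest reply is that the protocol already controls this. Section 10.1.3 wants the same method and modality throughout. Section 10.1.4.3 requires a new lesion to be unequivocal and not an effect of technique or modality. Section 10.1.2 has known disease, including a known pelvic primary, recorded and followed. A site that scanned by x-ray and MRI at baseline and then moved to CT would depart from Section 10.1.3, so footnote b does not license that switch.

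Much of this stands, and it rules out three inferences a reader might draw:

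- *That sites may change imaging freely at any scan.* Footnote b taken alone sets no limit on visits, but Section 10.1.3 does limit modality.
- *That the substitute both drops the pelvis and replaces chest CT with an x-ray.* The text names chest MRI as well. The chest rests on x-ray alone only if chest is a slip, and then the pelvis is covered.
- *That the 20 mm (x-ray) and 10 mm (CT, MRI) limits in Section 10.1.2 show thoracic progression would be missed.* They define measurability. An unequivocal new lesion is PD whether or not it is measurable.

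The reply does not reach coverage. The safeguards concern identified lesions and modality. Disease in an omitted region that is not known at baseline falls outside them, and the two sequences in Step 2 break none of them.

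**Conclusion.** The point holds as a gap in anatomical coverage, together with an internal contradiction in footnote b. Following the plan as written can miss progression or create it falsely in the primary endpoint.

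The size is uncertain because the documents do not say how often the substitute is used or how often progression first appears in the omitted region. If 5–10% of patients are read one scan late, alpha rises by about one percentage point, from 4.0% to 4.7–5.3%. False PD is the more costly error: 2–5% at week 12 takes power from 79% to 76–70%. These figures rest on exponential PFS, the assumed test and the assumed frequencies. The two errors act in opposite directions, and nothing makes them cancel.

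Two larger figures are tempting. A reader might note that one scan interval is 2.76 / 4 = 69% of the difference sought, but that sets one patient's delay against a difference in medians; one such delay moves the mean of 43 patients by 2.76 / 43 = 0.064 months. A reader might also start from a nominal 5% and get 5.8–6.7% for two to four late readings (shift of 2 or 4 × 2.76 × ln 2 / 8, divided by √43). That is again an increase of about one point; in simulation, 7% needs about 20% of patients one scan late. The planned N = 43 is not affected. The change should be made, but the unknown frequency does not support calling the trial's conclusion unsafe.

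**What to change.** Amend footnote b in Section 9 to:

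1. Reconcile the statement that all patients will have the CT with the statement that it is preferred, for example by making it the standard and stating when a substitute is allowed.
2. Replace the chest x-ray and MRI example.
3. State that any substitute must be cross-sectional, must cover chest, abdomen and pelvis at baseline and at every restaging, and must keep the patient's baseline modality and coverage throughout, consistent with Section 10.1.3.

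Leave Section 10.1.4.3 as it is. A reader might want to add a check against earlier imaging before PD is declared there. That would alter an explicit PD rule and add investigator judgement to an open-label endpoint, and fixed coverage makes it largely unnecessary.

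The cost is amendment wording, since full coverage is already the stated standard. Patients who cannot have the standard CT will need a substitute that also covers the pelvis. No extra visits or readers are needed.
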